6 STUDY INTERVENTIONS

6.1 Study Interventions

Control group (usual care). During the treatment phase of the study, each participant randomized to control will receive usual care from SLAAA, which includes annual NAPIS evaluation (in home) and individualized referrals to services based on identified need. Referrals are generated by case managers or SLAAA staff based on the annual assessment or if older adults (or their family members) call and request a referral for services.

Procedures for intervention (treatment). Participants who are randomized to treatment will receive usual care plus the home-modification (home-hazard removal) intervention. The intervention, based on a competence/press theoretical framework,⁹⁶ will be provided by registered and licensed OT. The intervention will be delivered via a manualized intervention using a visit by visit checklist. Home modifications⁷⁹ include a 2-hour home assessment conducted by an OT in the participant’s home using the WeHSA. A comprehensive clinical assessment will be performed on each participant to determine functional limitations that may interact with hazards in the home and result in a fall. Environmental hazards and unsafe behaviors will be identified. A barrier-removal plan will be provided to the older adult. The OT will facilitate home modifications through housing services programs and provided follow-up 2 weeks after the initial home visit to ensure that the participant adopted the recommended modifications. It is anticipated that 2-3 visits of 90 minutes each will be provided. At about 6 months participants will receive a booster session (in home visit by an OT) to reevaluate performance in the home and modify the intervention plan as needed.

Interventionist Training

Each interventionist will receive a 3 hour didactic training and additional 2 hours of guided self-directed learning.

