7.3.3 Intervention and follow up sessions

7.3.3.1 Intervention

Participants randomized to the intervention group will receive the intervention over 2 visits and one booster session at 6 months according to a manualized intervention. Briefly, for the intervention group, the occupational therapist will begin the intervention during the WeHSA. During the WeHSA the occupational therapist will assist the older adult to identify home hazards, work through potential solutions to reduce or remove the hazard, if possible, implement solutions (such as removing a throw rug), create plan for additional hazard removal, begin self-management training for behavioral and environmental fall risks, and provide training to complete the calendar journal. Between visits, the occupational therapist will assist the older adult to obtain equipment or home modifications. At the second visit, the occupational therapist will provide any necessary installation of equipment (such as a tub transfer bench), explain the purpose of each new equipment, teach techniques to safely use the equipment, and observe the older adult safely using the equipment. The occupational therapist will also continue the self-management training to improve daily activity performance and safety.

7.3.3.2 5 month adherence

A phone call to evaluate adherence will be made at approximately five months (in anticipation of the 6 month booster session).

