10.3 Data Analyses

We will examine the process data before the efficacy analyses.¹⁰⁷ We will use descriptive statistics to describe recruitment rates and reasons for not enrolling. To explore the extent and

[figure not shown]

Figure 6. Power calculation.

quality of the implementation of the intervention, we will compare the characteristics of patients who complete the assigned intervention with those who do not for differences in fall risks. Adherence and cost estimates will be conducted for participants in the intervention group. Descriptive statistics will be used for adherence. We will test the hypothesis that the intervention will have high acceptability (at least 80% retention), high fidelity by therapists (at least 95% of elements and at least 90% of dose delivered), and high adherence to the program (at least 80% of modifications in use) at 12 months. These hypotheses will be tested using a 1-sample 1-sided proportion test. For costs, initial analysis will be conducted to determine what type of approach will be necessary to make unbiased and relevant estimates of the cost of the intervention. We will compare the effectiveness of the program and usual care with the time to the first fall over 12 months as the primary outcome of interest. Survival analysis techniques will be used where time zero is the date on which the intervention is completed, and the ending time is 12 months after the intervention. Participants who do not have a fall will be censored at the end of the study. Participants who move to a nursing home will be censored on the date of moving. For those who fall during follow-up, the time to the first fall will be the event time. Kaplan-Meier product limit estimates will be used to describe the fall experiences for the intervention and control groups, with the log-rank statistic testing for significant difference. Prespecified covariates (e.g., age, race, sex, number of reported medications, mobility, ADL scores, and visual acuity) will be adjusted using the Cox proportional hazards model. We will test the interventions effect using the Cox proportional hazards model and adjusting for covariates. The regression coefficient of the indicator variable quantifies the difference in the log hazard of time to first fall between intervention and control groups. We will determine whether fall-prevention treatment is superior to usual care on secondary outcomes (total number of falls, number of injurious falls) and participant-reported outcomes (daily-activity performance, fall self-efficacy, and global health). We expect that the intervention group will experience fewer total falls, fewer injurious falls, greater daily-activity performance, greater self-efficacy, and greater quality of life compared with the usual care group.

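### The primary time-to-first-fall clock starts at completion of the intervention, a date that controls and intervention non-completers do not have, and no substitute date is given

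*Combined protocol and SAP*

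**What the plan says.** **Clock.** Section 10.3 (Data Analyses) makes time to first fall over 12 months the primary outcome. For the whole comparison, "time zero is the date on which the intervention is completed, and the ending time is 12 months after the intervention".

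**Who has that date.** Section 6.1 says that "each participant randomized to control will receive usual care from SLAAA"; the home-modification programme is added only in the other arm. Section 10.3 also expects some intervention participants not to complete: in the process evaluation, "we will compare the characteristics of patients who complete the assigned intervention with those who do not for differences in fall risks". Section 9 (Intervention Discontinuation) asks people who withdraw to continue their evaluations. It sets no start date and no analysis population.

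**What counts as completed.** Section 6.1 states: "It is anticipated that 2-3 visits of 90 minutes each will be provided". It then describes the booster at about 6 months separately. Section 7.3.3.1 says the intervention arm "will receive the intervention over 2 visits and one booster session at 6 months".

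**Follow-up elsewhere.** The opening design summary, Section 2.1 and Section 4 describe randomisation followed by 12 months of follow-up. The table in Section 7.5 has one follow-up column for months 1 to 12, and its footnote has both groups returning monthly fall journals.

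**Calendar start.** The therapist's first-visit tasks in Section 7.3.3.1 end with "and provide training to complete the calendar journal". Section 7.5 lists a Calendar Questionnaire at the consent visit. No start date for the fall calendar is given for either arm.

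**The concern.** Kaplan-Meier curves, the log-rank test and the Cox model need a start date for every participant. As written, the 150 planned controls have none, nor do the intervention non-completers. Someone must supply those dates, and nothing in the plan fixes the choice before outcome data are seen.

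The choice matters. Randomisation makes the arms comparable at randomisation. An origin that comes later, depends on what happened after allocation and exists in one arm only does not preserve that comparison. If higher-risk people leave the intervention arm's risk set before their clock starts, and their counterparts stay in the control arm, a programme with no effect can look beneficial.

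**Working it through.** **1. The plan's own power figure (Section 9.1, under heading 10).** Inputs: event-free proportions 0.39 (control) and 0.58 (intervention), 300 participants, 20% attrition, two-sided 5%.
- Hazards per year: -ln(0.39) = 0.9416 and -ln(0.58) = 0.5447. Ratio 0.5785, as stated.
- Evaluable: 300 × 0.80 = 240, or 120 per arm. Events: 120 × (0.61 + 0.42) = 123.6.
- Freedman: Φ(√123.6 × (1 − 0.5785)/(1 + 0.5785) − 1.96) = Φ(2.969 − 1.96) = 84.3%. The stated 84% reproduces.

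**2. First falls between randomisation and completion.** The documents do not give this lag. Section 6.1 puts a follow-up contact 2 weeks after the initial home visit, but the wait from randomisation to that visit is not stated. I assume 2 and 6 weeks. At the control hazard, the proportion is 1 − exp(−0.9416 × L):
- L = 2/52 year: 0.0356, about 5 of 150.
- L = 6/52 year: 0.103, about 15 of 150.

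**3. Illustration A: unequal clocks, no true effect.** Assumptions: control clock at randomisation, intervention clock at completion, earlier fallers not at risk, 12-month risk 61%, 150 per arm, gamma frailty variance θ.
- The marginal hazard is b/(1 + θbt), with b = (0.39^−θ − 1)/θ. For θ = 0.5, b = 1.2026 and θb = 0.6013.
- The hazard ratio at time t is (1 + θbt)/(1 + θb(t + L)). At L = 6 weeks it runs from 1/1.0694 = 0.935 at the start to 1.6013/1.6707 = 0.958 at 12 months. At 2 weeks it runs from 0.977 to 0.986.
- Simulation (20,000 runs, false benefit = z < −1.96):

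| Lag | Frailty variance | HR | One-sided false benefit |
|---|---|---|---|
| 2 weeks | 0.5 | 0.980 | 3.4% |
| 6 weeks | 0.5 | 0.945 | 5.4% |
| either | 0 | 1.00 | about 2.5% |

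Independent repeats with fewer runs gave up to 3.7% and 6.1%, hence about 3.5% and 5-6%. With randomisation as origin in both arms and variance 0.5, HR is 1.000 and false benefit 2.6%.

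**4. Illustration B: non-completers dropped, no true effect.** The plan does not state this exclusion; the proportions and hazard multiples are assumed. Control risk is held at 61%, 150 per arm, no attrition.

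| Non-completers' hazard | Dropped | HR | One-sided false benefit |
|---|---|---|---|
| 1.5 times | 10% | 0.961 | 4.4% |
| 1.5 times | 20% | 0.921 | 7.1% |
| 2 times | 10% | 0.932 | 6.6% |
| 2 times | 20% | 0.867 | 14.2% |
| equal | 20% | 1.002 | 2.3% |

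Hand check of the 2-times, 20% row: solve 0.8x + 0.2x² = 0.39, so x = 0.439 is the completers' event-free proportion. Events are 150 × 0.61 = 91.5 and 120 × 0.561 = 67.3. SE of log HR = √(1/91.5 + 1/67.3) = 0.161. Shift = ln(0.867)/0.161 = −0.89. Φ(−1.96 + 0.89) is about 14%.

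**5. Power if the clock starts at randomisation.** Worst case: the intervention arm keeps the control hazard until the visits are done. 120 per arm, 12 months, simulated: 85.5% with no lag, 80.8% at 2 weeks, 74.1% at 1 month, 69.0% at 6 weeks. With 150 per arm and 20% exponential attrition instead: 89.6%, 84.8%, 78.7% and 72.8%.

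**The case against.** The strongest reply is that the intent is recoverable. The design sections describe randomisation followed by 12 months of follow-up, and the Section 7.5 table gives both arms the same months 1 to 12, so a sensible analyst would use a common start. That shows a workable origin exists. It does not remove the conflict: Section 10.3 is the operative analysis rule and says something else.

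Three stronger readings are tempting, and the documents do not support them.
- **That the primary result will be biased.** Illustration A needs unequal clocks and Illustration B needs an exclusion, and the plan states neither. Frailty variance, hazard multiples, completion rates and lags are assumptions. At a 2-week lag the effect in Illustration A is small.
- **That non-completers will be excluded.** The sentence comparing completers with non-completers belongs to the process evaluation, and Section 9 asks people who withdraw to stay in evaluation. What is missing is a rule that keeps them in the analysis.
- **That completion means the 6-month booster**, which would make the lag and every figure far larger. One sentence in Section 7.3.3.1 groups the booster with the visits. But Section 5.2 (Study Enrollment Procedures) and Section 7.2 time assessments at 12 and 6 months after intervention, and Section 7.5 lists the booster separately from the treatment sessions, with falls collected over months 1 to 12. These treat the booster as falling within follow-up. The passages need reconciling, but they do not support sizing the problem on a 6-month lag.

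It is also fair to say that randomisation is not the only valid origin. Any common index date, defined identically in both arms and independent of completing visits, would close the gap.

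**Conclusion.** The time-zero rule is wrong as written. It cannot be applied to the control arm or to intervention non-completers, no substitute is given, and it conflicts with the follow-up described in the design sections. This holds without any simulation and should be corrected before the primary analysis.

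The size of any bias is conditional. It is nil under equal, constant fall risk. It is slight to modest with unequal clocks at 2- to 6-week lags and frailty variance 0.5 (HR about 0.98 to 0.95; false benefit about 3.5% to 5-6%). It is larger if 10-20% of the intervention arm, at 1.5 to 2 times the hazard, were dropped (HR about 0.96 to 0.87; about 4% to 14%). These figures show what the open choice could cost, not what the plan will do. The 84% power is not an error.

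**What to change.** Replace the time-zero sentence in Section 10.3 with:

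*Time zero is the date of randomisation in both arms. Every randomised participant is analysed in the assigned arm, whether or not visits were completed. First falls are counted for 12 months from that date.*

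Keep time from completion as a supportive analysis only, with completed defined and an index date stated for controls. Reconcile the Section 7.3.3.1 sentence on the booster with Sections 5.2 (Study Enrollment Procedures), 6.1, 7.2 and 7.5.

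Confirm that fall calendars start at randomisation in both arms. If they do, the cost is SAP wording. If they do not, falls just after randomisation are not recorded prospectively and wording alone will not suffice. In that case use one post-randomisation index date, defined identically in both arms and independent of completing visits.

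The downside is power. If there is no benefit until the visits are done, power from randomisation is about 81% at a 2-week lag, 74% at 1 month and 69% at 6 weeks. That is a worst case, because Section 7.3.3.1 allows some hazards to be removed at the first visit. State the 84% as conditional on no delay in effect. No new sample size is proposed.

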
11 DATA COLLECTION AND QUALITY ASSURANCE

11.1 Data Collection Forms

Data will be collected at each follow up point by a blinded rater over the phone. Data will be directly entered into an online data management software (see 11.2) Back up paper forms will be available (See MOP).

11.2 Data Management

Data-entry and data-management systems have been built to ensure accurate and complete data sets. Data will be entered via Web-based screens uploaded to a secure server. REDCap provides secure, Web-based applications, including real-time validation rules with automated data type and range checks at the time of data entry⁸¹. Data will be automatically backed up

daily, and copies will be stored offsite. All paper data forms will be reviewed weekly by the laboratory manager to ensure complete and accurate entry. Incomplete data will be returned to staff to rectify the situation by data edits, chart reviews, participant contact, or search of the National Death Index to ascertain status.

11.3 Quality Assurance

Training. Examples of quality assurance mechanisms include trained and certified field personnel,¹⁰⁸; comprehensive documentation of operations and procedures,¹⁰⁹ valid and accurate instrumentation (see “Outcomes and assessments”), field-tested data collection forms from our current HUD-funded study, a data-entry system with validation and checks⁸¹ with automated systems for scheduling and reminders, and quarterly audits of the database.

11.4 Quality-assurance oversight

QA oversight will be provided by the Washington University Human Research Quality Assurance (HRQA) program. The program will monitor this study to ensure the protection of human subjects and confirm that research is conducted in compliance with Federal regulations and university policies. In addition, study staff members ([name] and [name]) have undergone intensive training in quality assurance, quality control, ethics, and operations through the HRQA program. The PI and the study team will have access to continuing education, consultation, and quality-assurance procedures and forms. Quality assurance will ensure the successful activation of the research; the efficient and accurate collection of data to meet protocol objectives; and monitoring and auditing trial progress to ensure compliance with regulations, standards of operation, and subject safety.

11.4.1 Protocol Deviations

Protocol deviations will be captured on a protocol deviation form and reviewed by the study team and advisory board quarterly.

12 PARTICIPANT RIGHTS AND CONFIDENTIALITY

12.1 Institutional Review Board (IRB) Review

This protocol and the informed consent document (Appendix) and any subsequent modifications will be reviewed and approved by the HRPO committee responsible for oversight of the study. Informed Consent Forms

A signed consent form will be obtained from each participant. For participants who cannot consent for themselves, such as those with a legal guardian (e.g. person with power of attorney), this individual must sign the consent form. The consent form will describe the purpose of the study, the procedures to be followed, and the risks and benefits of participation. A copy will be given to each participant or legal guardian and this fact will be documented in the participant’s

record. we answered 'no' in myIRB questions on individuals lacking compacity to consent
Is this regarding folks who can't physically sign but understand?

12.2 Participant Confidentiality

Any data, forms, reports, photographs, and other records that leave the site will be identified only by a participant identification number (Participant ID, PID) to maintain confidentiality. All records will be kept in a locked file cabinet. All computer entry and networking programs will be done using PIDs only. Information will not be released without written permission of the participant, except as necessary for monitoring by IRB or HUD.

12.3 Study Discontinuation

The study may be discontinued at any time by the IRB or government agencies as part of their duties to ensure that research participants are protected.

13 PUBLICATION OF RESEARCH FINDINGS

Publication of the results of this trial will be governed by the policies and procedures developed by the Steering Committee. Any presentation, abstract, or manuscript will be made available for review by the sponsor.

15 SUPPLEMENTS/APPENDICES

15.1 Redcap data entry screen forms

15.2 IRB approval
